10.6 Vital Signs, Physical Findings, and Other Observations Related to Safety

10.6.1 Vital Signs

Descriptive statistics of vital signs results and change from baseline of vital signs will be summarized for the PP1 and PP2 samples. Data listings will be provided for vital signs measurements. They will be sorted by subject, vital sign parameter and time of assessment. Data reported in English units will be converted to corresponding metric units (e.g., cm, kg, degrees C).

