### **1.2 CLINICAL RATIONALE**

#### **1.2.1 Pediatric Liver Transplant Recipients**

Historically, the pediatric patient has been instrumental in the initial establishment of, and subsequent innovation in, the field of liver transplantation. Both the first attempted liver transplant in 1963 and the first successful liver transplant in 1967 involved young children. Later, during the late eighties and early nineties, special challenges facing pediatric liver transplantation motivated the development and refinement of innovative surgical strategies (i.e., reduced-size, split, and, finally, living-donor liver transplantation techniques) that have permeated and changed not only pediatric but also adult liver transplantation.

While these contributions have been predominantly surgical and technical in nature, pediatric transplant recipients may now present a unique opportunity to explore tolerance. Specifically, there now exists a significant number of stable living-donor recipients who underwent transplantation as children, typically from parent donors. The current trial proposes to identify a cohort of stable, pediatric living-donor recipients 4 or more years after transplantation who are willing to undergo gradual immunosuppression withdrawal under close and prolonged supervision with an aim to identify and quantify those who are tolerant—defined as those able to maintain normal allograft function in the absence of immunosuppression. Previous reports regarding prospective withdrawal

trials would suggest that a significant proportion of such patients can be successfully and safely withdrawn. Releasing young patients from the lifelong burden of immunosuppression has obvious benefit and appeal, particularly considering the reality that complications and toxicities of immunosuppression (e.g., renal dysfunction, infection, malignancy, metabolic abnormalities, and growth retardation) represent the major threats to long-term quality of life and survival in this posttransplant population.

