#### **5.5.3.3 Any Rejection Requiring Treatment**

If a participant experiences a single episode of mild rejection requiring treatment, or moderate or severe rejection, immunosuppression withdrawal will be discontinued. These participants will be considered to have failed immunosuppression withdrawal (see section 5.3). The algorithm for treatment of rejection is outlined in Figure 2. These definitions apply to the use of immunosuppressive agents for treatment of rejection:

**Reinstitution.** Returning to the regimen used before beginning immunosuppression withdrawal.

**Intensification.** Increasing the dose of immunosuppressant compared with that used before beginning immunosuppression withdrawal.

**Addition.** Initiating another nonsteroid immunosuppressant.

**Conversion.** Changing from one immunosuppressant to another.

**Steroid boluses.** Use of high-dose corticosteroids for a defined course, which may or may not be followed by an addition of corticosteroids to the maintenance immunosuppression regimen.

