### 6.2 GENERAL ASSESSMENTS

These general assessments will be performed (see Appendices 1–4):

- Informed consent. Written informed consent and subject assent (if applicable) will be obtained before performing any study assessments or procedures.
- Demographic history. A history will be taken to obtain the participant's date of birth, sex, race, and ethnicity.
- General medical history. A history will be taken to document any present or past diseases, any past or planned medical/surgical procedures, and information on the condition under study. Additionally, the most recent results of any previous testing of ALT or alkaline phosphatase and GGT will be documented.
- Liver transplant specific medical history. Rejection episodes, history of any cancer, CMV, infectious episodes, medication change histories, indication for liver transplantation, and results from any liver biopsy performed less than 1 year before screening. (If results for that period are not available, results of the most recent liver biopsy before screening will be collected).

- Physical examination.
- Vital signs. Temperature, blood pressure, pulse, respiration, weight, and height will be recorded.
- Review of inclusion and exclusion criteria.
- PPD skin test. A purified protein derivative (PPD) test to assess infection with tuberculosis will be performed at screening. Results of a prior test performed within 1 year prior to screening will be accepted in lieu of the test at screening and will be recorded on the case report forms (CRFs)
- Telephone consultation. Telephone consultations will be performed as scheduled to assess adverse events, changes in concomitant medications, and compliance with study therapy and laboratory assessments.
- Adverse events. Participants will be assessed for adverse events at all site visits. All adverse events will be recorded on the CRFs.
- Concomitant medications. All reported concomitant medications will be recorded on the CRFs.

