### **9.4.5 Safety**

All adverse events, including infections, malignancies, morbidity, and side effects associated with immunosuppression withdrawal and/or study participation, will be classified by body system and preferred term according to the *Medical Dictionary for Regulatory Activities* (MedDRA).

Frequency tables by category of event (e.g., serious, related to study participation, causing the discontinuation from the study) and by NCI-CTCAE grade will be presented. Laboratory values and vital signs will also be summarized by mean, standard deviation, and change from baseline.

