3.2.2 Secondary Endpoints

The following secondary endpoints are related to the safety of immunosuppression withdrawal.

- The proportion of subjects who have graft loss or who die after initiation of immunosuppression withdrawal.
- The time from the start of immunosuppression withdrawal to
 - the first episode of acute rejection requiring treatment,
 - the second episode of acute rejection not requiring treatment, or
 - the diagnosis of chronic rejection.
- The distribution of histologic severity among rejection episodes.
- The incidence of adverse events.
- Changes in renal function, blood pressure, cholesterol level, and glucose control.

Other secondary endpoints include

- Immunosuppression-free duration, defined as the time from discontinuation of immunosuppression to end of trial participation or to time of restarting immunosuppression;
- Results of mechanistic studies and clinical assessments at various time points that allow for the definition of profiles associated with tolerance;
- Results of mechanistic studies and clinical assessments that allow for definition of profiles associated with liver allograft rejection.

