- In the first column, if text wraps onto another line indent 1 additional space. For subgroups, indent 2 spaces.
- Units of measurement - International units SI will be used for clinical laboratory data as a standard presentation. The metric system will be used whenever possible. Thus, weight will be in kilograms and height in centimeters. Temperature will be presented in Celsius degrees.
- For general footnotes, 'Note:' will come before any bracketed footnotes.
- All listings will be sorted in order of treatment, subject, and time of assessment (e.g., visit, time, and/or event).
- Episodes of rejection will be determined by the diagnoses from the central pathologist. All references to rejection episodes in this Statistical Analysis Plan refer to central pathology reads.

If departures from these general conventions are present in the specific evaluations section of this SAP then those conventions will take precedence over these general conventions.

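### Height and weight are summarised only in raw cm and kg across a wide age range, so the planned tables of mean change mainly show who is still growing

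*SAP*

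**What the plan says.** Protocol 6.2 defines the vital signs: "Temperature, blood pressure, pulse, respiration, weight, and height will be recorded". They are scheduled at clinic visits in all four protocol appendices.

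Two places set out the analysis over time. SAP 10.6.1 says "Descriptive statistics of vital signs results and change from baseline of vital signs will be summarized for the PP1 and PP2 samples", adds listings, and converts English units to metric. Protocol 9.4.5 says "Laboratory values and vital signs will also be summarized by mean, standard deviation, and change from baseline". SAP section 4 fixes the scale: "Thus, weight will be in kilograms and height in centimeters".

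Elsewhere, height and weight appear as enrolment demographics, with BMI in a recipient listing (SAP 7.1), and height enters the GFR formula (SAP 10.4.5). Neither document mentions a z-score, percentile, growth velocity or growth reference.

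On the importance of growth, Protocol 1.2.1 says that "complications and toxicities of immunosuppression (e.g., renal dysfunction, infection, malignancy, metabolic abnormalities, and growth retardation) represent the major threats" to quality of life and survival in this population. Protocol 1.2.2 lists poor growth among the complications of progressive renal insufficiency in children. The change endpoint in SAP 3.2.2 does not include growth: "Changes in renal function, blood pressure, cholesterol level, and glucose control".

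**The concern.** A child who is growing too slowly still gains centimetres and kilograms, while an adult gains no height. When both are in one table, mean raw change depends first on the proportion still growing and only second on how well they grow. Normal ageing is not removed by a control arm, because there is none.

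The make-up of the table also changes over time. Participants who fail withdrawal are discharged after 52 weeks of medium-intensity follow-up (Protocol 5.3 and 6.6), so later visits hold a selected group. A shift in mean change between visits can come from that selection alone. The 10.6.1 summary is also not split by clinical phenotype, although the adverse-event tables (SAP 10.3) and the renal, blood pressure, cholesterol and glucose summaries (SAP 10.4.5) are.

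What is at stake is modest: a safety table on a complication that the protocol itself raises, filled with data collected for years, could not be read for growth.

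**Working it through.** **Inputs from the documents**
- Age: under 18 at transplantation and at least 4 years since then (Protocol 4.2). Consent tiers run from 4–6 years to 18 or older (Protocol 3.2). There is no upper age limit at entry.
- Size and design: 20 participants, single arm (Protocol 3.1).
- Follow-up of successes after withdrawal: 12 + 104 + 104 = 220 weeks (220/52 = 4.2 years), plus 208 weeks of extended follow-up = 428 weeks (8.2 years) (Protocol 6.6). The SAP states a minimum of 4 years (SAP 3.4), the protocol 8.
- Growth figures: none, so there is no plan figure to reproduce.

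**Assumptions, for illustration only**
- Those still growing gain g = 4 to 7 cm a year; those at full height gain 0.
- A share s = 0.50 to 0.75 of the 20 are still growing.
- The horizon is Y = 5 years, and growth slows by 20%.

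**Formulas**
- Normal mean change = s·g·Y
- Shift from 20% slowing = 0.2·s·g·Y
- SD from age mix alone = g·Y·√(s(1−s))
- 95% half-width of the mean = 2.093·SD/√20 (t with 19 df)

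**Results (cm over 5 years)**

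| g | s | Normal mean | Mean if 20% slower | Shift | SD from mix | Half-width |
|---|---|---|---|---|---|---|
| 4 | 0.50 | 10.0 | 8.0 | 2.0 | 10.0 | 4.68 |
| 4 | 0.75 | 15.0 | 12.0 | 3.0 | 8.66 | 4.05 |
| 7 | 0.50 | 17.5 | 14.0 | 3.5 | 17.5 | 8.19 |
| 7 | 0.75 | 26.25 | 21.0 | 5.25 | 15.16 | 7.09 |

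In every row the half-width from age mix exceeds the shift. The ratio of the two is 2.093·√((1−s)/s)/(0.2·√20) = 2.34·√((1−s)/s). It does not depend on g or Y, so the choice between the SAP's and the protocol's follow-up length does not matter. It is 2.34 at s = 0.50 and 1.35 at s = 0.75, and falls to 1 at s = 0.85.

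**Composition.** If the share still growing falls from 75% to 50% between two tables, the normal five-year mean falls from 15.0 to 10.0 cm (g = 4) or from 26.25 to 17.5 cm (g = 7). That is a drop of one third with nobody's growth altered, which is more than the 20% slowing.

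**Limit of the illustration.** If all 20 are growing, this two-level model has no age-mix variation and the half-width comparison does not apply. Even then, a 20% slowing gives the same mean as 80% growing normally: 0.8 × 20 = 16 cm, or 0.8 × 35 = 28 cm. The half-width is only a yardstick, since the SAP plans descriptive statistics here and no interval.

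**The case against.** Growth is in no objective and no endpoint of either document. It is one item in a parenthesis of examples in Protocol 1.2.1, and the rationale for the study population (Protocol 3.4) names renal dysfunction, hypertension and metabolic abnormalities instead. Section 10.6.1 is a routine safety tabulation from which no growth claim is planned. This stands, and it sets the weight of the point.

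A reader might infer that the trial could not detect impaired growth at all. The documents do not support that. Vital signs are listed by subject and time, and birth date and sex are listed by subject (SAP 7.1). A growth disorder reported as an adverse event would be coded and tabulated, and 20 trajectories can be read individually. The gap is in the summary tables. Scores could be derived later, but the reference and method would then be chosen with the data in hand.

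A reader might also infer a missed growth harm from corticosteroid rescue, which Protocol 5.5.3.3 describes as "Use of high-dose corticosteroids for a defined course, which may or may not be followed by an addition of corticosteroids to the maintenance immunosuppression regimen". No passage links corticosteroids to growth. Participants who fail withdrawal have vital signs scheduled only at M6 and M12 of their 52-week follow-up, so little would show on any scale. That argument is not part of this point.

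SAP 9.4 rules out subgroup analyses. Clinical phenotype is, however, a declared grouping for selected analyses (SAP 3.3), so a descriptive split by phenotype is consistent with the plan.

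**Conclusion.** The point holds as a low-weight one. The only planned summaries of height and weight over time are raw and unadjusted for age and sex, in a group that can run from four-year-olds to adults, so mean change mainly reflects the age mix at each visit. Under the assumed rates, with 50% to 75% still growing, age mix alone blurs the mean by 1.35 to 2.34 times the shift from a 20% slowing. The actual size depends on the ages enrolled, which the documents do not give.

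No primary or named secondary endpoint is affected. A reader might expect standardised scores to show a growth benefit of withdrawal. They would not: with one arm of 20 and phenotype defined by outcome, they support description only, not attribution.

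**What to change.** In SAP 10.6.1, name a growth reference. For participants within its age range, derive age- and sex-specific z-scores for height, weight and BMI. Summarise the z-score and its change from baseline by visit, overall and descriptively by clinical phenotype, following the layout that SAP 10.4.5 already uses for renal function and blood pressure. Give the number contributing at each visit. Raw centimetres and kilograms may stay beside the scores. State that the summary is descriptive.

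The cost is a few lines of SAP text and programming. Birth date, sex, height and weight are already collected, and no visit, assessment or clinical rule changes. The SAP already adjusts for age and sex in one place, the constant in its GFR formula.

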10.6.2 Physical Examinations

A listing of the physical examination data will be created. Physical exam status at baseline and change in physical examination will be summarized at each post-baseline visit by body system. The categories of change include no change, improved, and worsened.

11. EXPLORATORY ANALYSES

All analyses performed on the PP2 sample will also be performed on the PP2 sample excluding subjects with selected liver pathologies as exploratory analyses.

12. OTHER ANALYSES

12.1 Use of Medications

Medications reported on the CRF will be categorized into prior, concomitant or after for analysis. Prior, concomitant or after medications will be identified by comparing the medication start and stop dates with the date of initiation of immunosuppression withdrawal. Prior medications will have both the medication start and stop date prior to the first dose of study medication date. After medications will have both the medication start and stop date after the last dose of study medication date. All other medications will be classified as concomitant, indicating that use of the medication overlapped with use of the study medication by at least one day.

The number and percentage of subjects receiving prior, concomitant and after medications will be presented overall and by medication class. When reporting the number of subjects receiving the medication, a subject will only be counted once if they ever received the medication within the medication class. Percentages will be based on the number of subjects in the PP1 sample. Separate data listings will be provided for prior, concomitant and after medications.

12.2 Immunosuppression Medication History

Number and percentage for types of medication given during induction, given post-discharge, and used within the 12 months prior to enrollment will be summarized for all subjects by visit in the ITT sample. Separate data listings will be provided for induction, post-discharge, and detailed 12 month prior to enrollment to current immunosuppression.

12.3 Medical History

The number and percentage of subjects with clinically significant diseases including allergies and current or past medical procedures other than the disease under study, by body system will be listed and summarized for the ITT sample.

12.3.1 Liver Transplant Specific Medical History

The liver transplant specific medical history includes indication for liver transplant, whether subject has experienced infections associated with liver transplant and the infection type, and whether subject has experienced malignancy since the liver transplant. A data listing will be created for liver transplant specific medical history data for the ITT sample.

12.3.2 Rejection History

Rejection episode date, histological grading and treatment for rejection will be listed for all rejection history for the ITT sample.

12.3.3 Prescreening Biopsies

Reason for biopsy, BANFF global assessment grade, other findings and Ishak fibrosis score will be listed for all pre-screening biopsies for the ITT sample.

12.3.4 Blood Typing

The number and percents for blood type and Rh type for all subjects and their donors will be summarized. Blood typing data for all subjects in the ITT sample and their donors will also be listed.

13. INTERIM ANALYSES AND DATA MONITORING

Per protocol version 4.0, there are not any planned interim analyses for this study.

The protocol chair, the ITN clinical trial physician, the NIAID medical monitor, and the NIAID Transplant Data and Safety Monitoring Board (DSMB) will periodically review safety data. Enrollment of subjects in the trial and withdrawal of immunosuppression in current trial subjects will be suspended at any time if any of these reviews concludes that there are significant safety concerns. Stopping rules are described in Section 3.5 of the protocol.

The progress of the study will be monitored by the NIAID Data and Safety Monitoring Board (NIAID DSMB). The NIAID transplant DSMB will be chartered to review safety data and to make recommendations regarding continuation, termination, or modification of the study. The DSMB will formally review the safety data at least yearly. The discontinuation of study treatment will also be periodically reported to the DSMB.

In addition, safety data will be reviewed by the DSMB when an event occurs that is of sufficient concern to the NIAID medical monitor or protocol co-chairs to warrant review, or when an event occurs that could contribute to a pre-defined stopping rule specified in the Protocol.

Findings will be reported to IRBs and health authorities.

14. CHANGES TO THE ANALYSES PLANNED IN THE PROTOCOL

The principal features of the plan for statistical analysis of the data are outlined in this SAP. Any changes in these principal features will require a SAP amendment, which will be subject to review by the independent DSMB, the study sponsor(s), and the regulatory agencies. These changes will be described in the final report as appropriate.

16. APPENDICES

16.1 Schedule of Events

Appendix 1. Schedule of Events: Gradual to Complete Withdrawal Plus 3 Months of High-intensity Follow-up

	Withdrawal Plus 3-Month High-intensity Follow-up														
Monthly visits	-2	-1	0	1	2	3	4	5	6	7	8	9	10	11	12
				13	14	15	16	17	18	19	20	21	22	23	24
General Assessments															
Informed consent	X														
Demographic history	X														
Medical history	X														
Liver transplant: specific medical history	X														
Physical examination	X	X				X			X			X			X

	Withdrawal Plus 3-Month High-intensity Follow-up														
Monthly visits	-2	-1	0	1	2	3	4	5	6	7	8	9	10	11	12
				13	14	15	16	17	18	19	20	21	22	23	24
Vital signs	X	X				X			X			X			X
Inclusion/exclusion criteria		X													
PPD skin test	X														
Telephone consultation			X	X	X		X	X		X	X		X	X	
Adverse events		X	X	X	X	X	X	X	X	X	X	X	X	X	X
Concomitant medications	X	X	X	X	X	X	X	X	X	X	X	X	X	X	X
Study Site and Local Laboratory Assessments															
Hematology	X ¹					X			X			X			X
Comprehensive chemistry	X ¹														X
Basic chemistry						X			X			X			
Liver panel		X	Every 2 weeks starting at visit 0 ²												
Autoantibodies	X					X			X			X			X
Quantitative immunoglobulins	X					X			X			X			X
Viral serology ³	X														
Urine hCG	X														
Glomerular filtration rate (creatinine and height)	X														
Hemoglobin A _{1c}	X														
Tacrolimus or cyclosporine serum levels		X													
Central Laboratory Assessments															

¹ Can be performed within 9 weeks before the liver biopsy visit.

² LFTs must be performed upon diagnosis of allograft dysfunction or rejection and at the resolution of rejection (see sections 5.5.2 and 5.5.3.1). Additional LFTs may be performed during rejection at the investigator's discretion.

³ See section 6.3 for a description of the viral tests to be performed.

	Withdrawal Plus 3-Month High-intensity Follow-up														
Monthly visits	-2	-1	0	1	2	3	4	5	6	7	8	9	10	11	12
				13	14	15	16	17	18	19	20	21	22	23	24
Whole blood–quantitative PCR for CMV reactivation	X					X			X			X			X
Whole blood–quantitative PCR for EBV reactivation	X					X			X			X			X
Liver Biopsies															
Liver biopsies ⁴		X													X ^{5,6}
Tolerance Assessments⁷															
Whole blood–flow cytometry panel staining	X ⁸					X			X			X			X
Frozen PBMC–T-cell assays ⁹	X ⁸					X			X			X			X
Liver biopsy–histology		X													X ^{5,6}
Whole-blood–gene expression profiling	X ⁸					X			X			X			X
Liver biopsy RNA–gene expression profiling		X													X ^{5,6}
Serum–secreted cytokines	X ⁸					X			X			X			X
Serum–HLA alloantibodies	X ⁸								X						X
Whole blood DNA–HLA genotypes ^{9, 10}	X ⁸														

⁴ Additional biopsies will be done to rule out rejection if necessary.

⁵ Will be performed within 4 to 8 weeks after the last dose of immunosuppressant is taken.

⁶ Will be performed only at visit 12 and not at visit 24.

⁷ If a rejection episode occurs, samples for all mechanistic assessments that are scheduled for monthly visits 12 and 24 (except for whole blood–flow cytometry panel staining) will be collected at this time.

⁸ Please try to collect blood at assigned visit -2; if this is not possible, collect at visit -1. If not able to collect at visit -1, please collect at visit 0.

⁹ To be collected from living donor and nondonor parents after they have signed the informed consent; blood draw can be done at any visit during the recipient’s trial participation.

¹⁰ Collection from the subject may be deferred to any visit during the trial depending on subject’s weight and blood volume status.

